7.4.8. Symptom Response/Quality of Life

A symptom response instrument will be used to evaluate symptoms specific to NIH Quality of Life and Symptoms Questionnaire for Pheochromocytoma and Paraganglioma. The questionnaire is administered twice during the baseline period prior to the first therapeutic dose. The results of the two responses will be averaged by item and will be treated as the baseline values. Results by item will be summarized for the Full Analysis Set, and questionnaire data will be listed.

The EORTC QLQ-C30 v.3^[3] will be used to evaluate QoL. The questionnaire is administered twice during the baseline period prior to the first therapeutic dose. The last non-missing values obtained closest to dosing will be treated as the baseline values. The results of QoL and changes from baseline will be summarized by visit and domain across the Full Analysis Set and will be listed. This data will be summarized as follows: Global Health Status/Quality of Life, Functional Scales, and Symptom Scales. The best response within 12 months after first therapeutic dose will also be reported.

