11.5.14 Symptom and Quality of Life Evaluations

Two questionnaires and two clinical evaluations will be employed to evaluate the clinical status of each subject.

Quality of Life will be measured by subject report using the EORTC QLQ-C30 v.3 (Appendix IV). Also, the NIH Quality of Life and Symptoms Questionnaire for Pheochromocytoma and Paraganglioma (Appendix IV) will be used to evaluate symptoms specific to pheochromocytoma or paraganglioma. Both of these subject-reported questionnaires will be administered at Screening/Baseline (twice) before the first therapeutic dose, Week 3, Week 6, Week 10, Week

12, Week 15, Week 18, Week 22, and monthly from 6-12 months following the first Therapeutic Dose.

The Karnofsky Performance Status Scale (Appendix I) will be completed by the Investigator at screening/baseline, the day of each Therapeutic Dose, at the safety visits 6 weeks after each Therapeutic Dose and at the efficacy visits in months 3, 6, 9 and 12 post the first Therapeutic Dose. The Karnofsky Performance Status Scale administered at 6 weeks after each Therapeutic Dose administration may occur within ± 10 days of the Week 6 window to accommodate potential blood count nadir or travel restrictions. The Investigator will evaluate the subject's clinical status at each timepoint as compared to baseline measurement.

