5	Symptom Response (NIH Pheochromocytoma Clinical Questionnaire) and EORTC QLQ-30 Questionnaire	Screening / Baseline (Day -28 to Day 0) Note: two assessments are to be performed prior to the first therapeutic dose within this window	Week 3 (Day 15 - Day 21) Week 6 (Day 36 - Day 42) Week 10 (Day 64 - Day 70) Week 12 (Day 78 - Day 84) Week 15 (Day 99 - Day 105) Week 18 (Day 120 - Day 126) Week 22 (Day 148 - Day 154) Month 6 (Day 173 - Day 193) Month 7 (Day 203 - Day 223) Month 8 (Day 233 - Day 253)	

No	End Point	From Imaging Dose 1	From Therapeutic Dose 1	From Therapeutic Dose 2
			Month 9 (Day 264 - Day 284) Month 10 (Day 294 - Day 314) Month 11 (Day 325 - Day 345) Month 12 (Day 355 - Day 375)	
6	Tumor Pain Medication		Month 3 (Day 81 - Day 101) Month 6 (Day 173 - Day 193) Month 9 (Day 264 - Day 284) Month 12 (Day 355 - Day 375)	

Safety Assessments

No	End Point	From Imaging Dose 1	From Therapeutic Dose 1	From Therapeutic Dose 2
1	Vital Signs (pulse, temperature, respiration)	Screening / Baseline (Day -28 to Day 0) Day 1: 4 hours prior Day 1: 4 hours post	Day 1: 4 hours prior Day 1: 4 hours post	Day 1: 4 hours prior Day 1: 4 hours post
2	Vital Signs (body weight)	Day 1: prior to dosing	Day 1: prior to dosing	Day 1: prior to dosing
3	Vital Signs (BP and heart rate by Health Staff and Subject Readings)	Screening / Baseline (Day -28 to Day 0) Day 1: 4 hours prior Day 1: 4 hours post	Day 1: 4 hours prior Day 1: 4 hours post Week 1 (Day 2 - Day 7) 2x week Week 2 (Day 8 - Day 14) 2x week Week 3 (Day 15 - Day 21) 2x week Week 4 (Day 22 - Day 28) 2x week Week 5 (Day 29 - Day 35) 2x week Week 6 (Day 36 - Day 42) 2x week Week 7 (Day 43 - Day 49) Week 8 (Day 50 - Day 56) Week 9 (Day 57 - Day 63) Week 10 (Day 64 - Day 70) Week 11 (Day 71 - Day 77)	Day 1: 4 hours prior Day 1: 4 hours post Week 1 (Day 2 - Day 7) 2x week Week 2 (Day 8 - Day 14) 2x week Week 3 (Day 15 - Day 21) 2x week Week 4 (Day 22 - Day 28) 2x week Week 5 (Day 29 - Day 35) 2x week Week 6 (Day 36 - Day 42) 2x week Week 7 (Day 43 - Day 49) Week 8 (Day 50 - Day 56) Week 9 (Day 57 - Day 63) Week 10 (Day 64 - Day 70) Week 11 (Day 71 - Day 77)

No	End Point	From Imaging Dose 1	From Therapeutic Dose 1	From Therapeutic Dose 2

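### SAP 7.4.8 reports an undefined, unconfirmed best QLQ-C30 response over up to 14 questionnaires; read as change from baseline, it would show improvement in many subjects with no true change

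*SAP*

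**What the plan says.** SAP 7.4.8 (Symptom Response/Quality of Life) takes a single pre-dose questionnaire as the QLQ-C30 baseline, although two are collected: "The last non-missing values obtained closest to dosing will be treated as the baseline values". The main summary follows: "The results of QoL and changes from baseline will be summarized by visit and domain across the Full Analysis Set and will be listed". The section then adds: "The best response within 12 months after first therapeutic dose will also be reported".

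Nothing in the SAP says what this best response is. There is no named score or category, no threshold, no confirmation rule and no stated reference to baseline. The list of planned tables has QLQ-C30 tables for global health status, functional scales and symptom scales (14.2.4.1 to 14.2.4.3), and none named for best response. Protocol 13.3.2.2.4 asks only for results and changes from baseline by domain, so the best-response figure is an addition made in the SAP.

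The questionnaire is given often. Protocol 11.5.14 lists Weeks 3, 6 and 10, then Week "12, Week 15, Week 18, Week 22, and monthly from 6-12 months following the first Therapeutic Dose". SAP Appendix 1 has matching windows, from "Week 3 (Day 15 - Day 21) Week 6 (Day 36 - Day 42) Week 10 (Day 64 - Day 70" through to "Month 9 (Day 264 - Day 284) Month 10 (Day 294 - Day 314) Month 11 (Day 325 - Day 345" and Month 12.

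**The concern.** The quality-of-life objective is to describe change from baseline after treatment. A subject's score moves up and down between visits even when the underlying state is constant. Picking the best of many such scores and setting it against one earlier score selects the favourable fluctuations, so the result is positive on average with no treatment effect.

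Two features of this plan add to the difficulty. The trial is open-label and single-arm, so no control group would show the same apparent gain. And the SAP guards its other responses: CR, PR and MR on imaging need a repeat assessment at least four weeks later (7.4.5), and tumour marker responses must be confirmed (7.4.7). The QLQ-C30 figure has no such guard, although it is self-reported and collected more often than the scans. It would also show a subject who felt well once and then declined at that subject's peak.

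At stake is one reported figure that could be read as benefit. The trial's success criterion is not affected.

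**Working it through.** The documents state no expected value for this statistic, so there is no planned figure to reproduce.

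**Number of questionnaires.** Weeks 3, 6, 10, 12, 15, 18 and 22 make 7; Months 6 to 12 make 7; 7 + 7 = 14. Protocol 11.5.14, the Appendix VII table and SAP Appendix 1 agree. Footnote 13 of Appendix VII omits Week 15, which would give 13.

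**Idealised share above baseline.** With no true change and k + 1 exchangeable, untied scores (one baseline and k post-dose), each score is equally likely to be the highest. So P(best post-dose > baseline) = k/(k + 1), whatever the correlation between visits:

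- k = 14: 14/15 = 93.3%
- k = 13: 13/14 = 92.9%
- k = 8: 8/9 = 88.9%
- k = 4: 4/5 = 80%
- k = 1 (one fixed visit): 1/2 = 50%

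**Idealised mean gain.** For normal scores with equal correlation ρ, the subject's own level cancels, leaving SD × √(1 − ρ) × E(maximum of 14 standard normals), where the last term is 1.70. In SD units this is 1.20 at ρ = 0.5, 0.93 at ρ = 0.7 and 0.54 at ρ = 0.9. With an assumed SD of 22 points:

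- ρ = 0.5: 22 × 0.707 × 1.70 = 26.4
- ρ = 0.7: 22 × 0.548 × 1.70 = 20.5
- ρ = 0.9: 22 × 0.316 × 1.70 = 11.8

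**Realistic global health score.** Items 29 and 30 are each scored 1 to 7, so their sum runs from 2 to 14: 13 levels, with a floor and a ceiling. I rescaled this to 0-100 and simulated 200,000 subjects per setting with no true change and all 14 forms completed. Assumptions not in the documents: mean 60 or 75, SD 22, between-visit correlation (ICC) 0.5 to 0.9, and further serial correlation with a time constant of 0, 30 or 90 days. Extremes of the serial correlation are shown:

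| Mean | ICC | Above baseline (0 / 90 days) | Mean best change, points (0 / 90 days) |
|---|---|---|---|
| 60 | 0.5 | 87% / 82% | 24.4 / 19.1 |
| 60 | 0.7 | 85% / 79% | 19.2 / 15.0 |
| 60 | 0.9 | 79% / 71% | 11.3 / 8.7 |
| 75 | 0.5 | 78% / 74% | 20.1 / 16.2 |
| 75 | 0.7 | 76% / 71% | 16.2 / 12.8 |
| 75 | 0.9 | 70% / 63% | 9.8 / 7.7 |

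Over all settings, 63-87% appear improved, 25-74% by at least 10 points, and the mean false gain is about 8-24 points. For a four-level single item (mean 60 or 80) the share is 22-66%.

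**Contrast with one fixed visit.** Under the same assumptions, one prespecified visit gives a mean change of 0, with 30-42% above baseline on the global score.

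**Does the baseline choice matter?** One form and the mean of two have the same expectation when nothing changes, so the expected gain is the same: 1.20 SD either way at ρ = 0.5 and 0.93 SD either way at ρ = 0.7, for 14 forms. The share above baseline rises with averaging, from 93.3% to 97.3% with 14 forms and from 88.9% to 93.9% with 8, because a less variable baseline is easier for a maximum to beat.

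**The case against.** The strongest reply is that little depends on this sentence. The best response is reported in addition to by-visit changes, which do not pick the favourable visit. Quality of life is a descriptive secondary endpoint without a test or success rule. Later decline is not hidden: Protocol 9.8 keeps discontinued subjects who have not withdrawn consent on scheduled assessments other than scans and marker tests, and deaths enter overall survival. All of this stands and limits the weight of the point. It does not make the figure sound, and the SAP commits to reporting it.

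It can also be said that comparison with baseline is not stated. That is true: a best absolute score is possible. But the objective is change from baseline, so that is the natural reading, and a statistic open to both readings needs a definition in any case.

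A reader might infer that nearly everyone would appear improved on every scale. The documents do not support that. The 93% needs untied, unbounded scores and complete forms. The items have four or seven levels, ties do not count as gains, a subject with no symptom at baseline cannot improve on it, and missed forms lower the share.

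A reader might also infer that using only the last pre-dose form makes the bias worse, because the NIH questionnaire in the same section does otherwise: "The results of the two responses will be averaged by item and will be treated as the baseline values". The calculation above shows that it does not. The different baselines are an unexplained inconsistency, separate from this bias.

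**Conclusion.** The point holds, for this supplementary figure only. SAP 7.4.8 commits to an undefined, unconfirmed best QLQ-C30 response over up to 14 questionnaires. Read as change from baseline, it would show improvement in a large share of subjects with no true change: up to 93% in the idealised case, and roughly 63-87% on the global health score with a mean false gain of about 8-24 points. The single-arm design offers nothing to set against that.

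The upward direction follows from taking a maximum and does not depend on the assumed values. The sizes do: they rest on the assumed SD of 22, correlation of 0.5-0.9, mean of 60 or 75, and all 14 forms being completed. The by-visit changes, the primary analysis and the trial's success criterion are untouched.

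**What to change.** Delete the best-response sentence for the QLQ-C30 in SAP 7.4.8. Name change from baseline in global health status at Month 6 and Month 12, already within the by-visit tables, as the headline values. Optionally add each subject's mean change over all completed post-dose questionnaires, which does not select the best visit.

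If a best-response figure is kept, define it (scale, direction, reference to baseline, threshold), require confirmation at the next questionnaire, and print beside it the value expected with no true change. Confirmation reduces the selection but need not remove it.

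Separately, averaging the two pre-dose questionnaires would make the by-visit changes more precise and match the NIH instrument. It should not be offered as a remedy for the best-response bias.

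The cost is a short SAP edit and minor programming, with no new data collection. The downside for the sponsor is that the reported figure becomes less favourable.

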7.4.9. Tumor Pain Medicine

Pain medication used to relieve tumor pain will be defined as medication identified in the case report form to relieve tumor pain.

A shift table for tumor pain medication usage by subject will be presented by visit, with pain medication usage categorized into three intensity levels: any opioid use, other pain medication use, and no pain medication use. This categorization will be made based on usage at 3 months (91 days), 6 months (182 days), 9 months (273 days), and 12 months (365 days) post first therapeutic dose. Analgesics identified for other uses will not be included in this summary.

A separate listing of analgesic medications other than those used for tumor pain reduction will be provided.

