13.3.2.2.6 Analgesics and pain medicine

Changes in total dose of any single medication used to control tumor pain, and changes in potency within a symptom treatment (e.g., conversion of narcotic to NSAID) will be evaluated by subject and across the Full Analysis Set.

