4.3. Trial Objectives: Secondary

The secondary objectives of this trial are as follows:

- To evaluate the safety of iobenguane I 131 in subjects with malignant pheochromocytoma/paraganglioma, including human radiation absorbed dose estimates to normal organs.
- To assess the proportion of subjects with overall tumor response of CR or PR per RECIST criteria.
- To assess the proportion of subjects with overall tumor response of CR, PR or MR (moderate response, i.e., decrease in the sum of the longest diameters of the target lesions of 15-30%, with no evidence of progressive disease [PD] in non-target lesions) per RECIST criteria.
- To assess status of bone lesions using the Soloway Scale.
- To assess tumor marker response in 24 hr urine and other serum tumor markers associated with pheochromocytoma/paraganglioma.
- To describe changes from baseline in the overall QoL through the EORTC QLQ-C30 questionnaire post-treatment.
- To describe changes from baseline in symptoms using the NIH Quality of Life and Symptoms Questionnaire for Pheochromocytoma and Paraganglioma post-treatment.
- To assess change in use of analgesics and pain medications.
- To describe Karnofsky Performance Status post-treatment.
- To assess overall survival, up to 5 years post-treatment.

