7.7. Procedures for Handling Dose and Dosing Frequency (Anti-hypertensive and Pain Medications)

In order to standardize the reporting of doses and dose frequency, all unique values of these fields from the raw concomitant medication dataset will be exported to an Excel spreadsheet where the total daily dose will be added to create a coded dataset. The Excel sheet will be prepared by the Sponsor and used in the creation of analysis datasets. This standardization will be applied to medications identified as anti-hypertensive medications on the CRF and, separately, to medications identified as analgesics with indications for pain relief

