9. CHANGES FROM VERSION 1.0 OF SAP

The following are a summary of changes from those specified in Version 1.0 of the SAP (16 November 2009). Additional changes from Version 3.0 to 4.0 of this SAP are indicated at the end of this table.

Section	Version	Change
5.1	5.0	Clarification of handling of subjects with multiple enrollments
6	5.0	Removal of identification of per-protocol population
7.0	2.0	Time to event analyses added to statistical methods section.
7.0	5.0	Clarification of period definitions
7.2.4	2.0	New section added to reference imaging listings.
7.1	4.0	Addition of visit windows for summaries
7.3.1	2.0	Clarifications and additional details added to define algorithms for primary endpoint duration and for 50% reduction in antihypertensive medication use.
7.2.3.2	5.0	Update in MedDRA dictionary version
7.3.2	5.0	Update in WHO Drug Dictionary version
7.3.4	2.0	Listing of tumor response, clinical benefit status, and % change in CgA added.
7.3.6	2.0	Correlations between tumor change from baseline and tumor response, and among tumor markers added.
7.3.7	3.0	Section for tumor marker trend analysis deleted, all subsequent sections renumbered.
7.3.8	3.0	NIH Questionnaire reporting limited to reporting by item by visit.
7.3.9	2.0	Shift tables of pain medication use added. Comparisons of changes in potency using narcotic to NSAID conversions deleted.
7.3.11	2.0	Overall survival algorithm changed to reference date of first therapeutic dose as opposed to informed consent date.
7.3.12	2.0	New section added for site assessment of disease.
7.4.1	5.0	Definition of end of assessment period for subjects who terminate the study early, clarification of blood pressure measurements to be presented in figures by subject, clarification of clinical benefit period.
7.4.2	5.0	Added section with calculation of the primary endpoint, which was Appendix 1.
7.4.4	3.0	Threshold for reporting most frequent adverse events increased to 20% from 5%.
7.4.5	5.0	Clarification of objective tumor response criteria
7.4.7	5.0	Clarification of tumor marker analyses, change in correlation measures from percent change from baseline to tumor marker response, addition of a binary response comparison
7.4.8	5.0	Change in definition of baseline values
7.4.9	2.0	Added reporting for estimated creatinine clearance, including classification of values into estimates of renal function added.

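### Change in tumor-pain medication is summarized only as any opioid / other / none, so within-category dose changes count as no change and the protocol's dose evaluation is dropped without explanation

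*SAP*

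**What the plan says.** The secondary objective, in both documents, is "To assess change in use of analgesics and pain medications" (quoted here from SAP 4.3).

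Protocol 13.3.2.2.6 states what is to be evaluated: "Changes in total dose of any single medication used to control tumor pain, and changes in potency within a symptom treatment". It asks for this per subject and over the Full Analysis Set.

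SAP 7.4.9 plans a shift table by visit, with "pain medication usage categorized into three intensity levels: any opioid use, other pain medication use, and no pain medication use". The categories are assigned at "3 months (91 days), 6 months (182 days), 9 months (273 days), and 12 months (365 days) post first therapeutic dose". Dose does not enter the rule. The matching output in SAP 11 is Table 14.2.7, and no dose-change table is listed for pain medication.

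SAP 7.7 standardizes dose and frequency so that "the total daily dose will be added to create a coded dataset". This applies to antihypertensives and, separately, "to medications identified as analgesics with indications for pain relief".

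The SAP 9 change log has an entry, at version 2.0, for the pain-medication section. It says that shift tables were added, and then: "Comparisons of changes in potency using narcotic to NSAID conversions deleted". It says nothing about change in total dose.

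**The concern.** The protocol names dose as the quantity to follow. The SAP derives dose and then does not use it to summarize change. A shift table on three levels registers a change only when a subject crosses a boundary between levels. A subject who stays on an opioid at a much lower or much higher dose is reported as unchanged, and so is a subject whose non-opioid dose changes greatly.

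What is at stake is the interpretability of one secondary endpoint. Dose reduction in subjects who stay on medication could reflect palliation, and dose escalation could reflect worsening. The planned aggregate output shows neither. There is also a traceability issue: a protocol-stated evaluation has no counterpart in the SAP and no stated reason for its absence.

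**Working it through.** The plan gives no figure to reproduce, because no sample size, alpha or test is attached to this endpoint. The check is a comparison of sections and an application of the SAP rule.

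**1. The sections side by side**

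| Item | Protocol | SAP |
|---|---|---|
| Change in total dose per tumor-pain drug | Evaluated (13.3.2.2.6) | Not summarized in 7.4.9 or in any table in 11 |
| Change in potency | Evaluated (13.3.2.2.6) | Conversion comparison removed, and logged (9) |
| Total daily dose for analgesics | Dose recorded throughout (9.1) | Derived (7.7) |
| Summary of change | Per subject and over the Full Analysis Set | Three-level shift table only (7.4.9, Table 14.2.7) |

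**2. The SAP rule applied**

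For this check, code any opioid as 2, other pain medication only as 1, and none as 0. Then shift = follow-up code − baseline code, and percent change = 100 × (follow-up − baseline) / baseline. The doses are assumed, in arbitrary mg per day of a single drug, because the documents give none.

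| Baseline | Follow-up | Dose change | Shift |
|---|---|---|---|
| Opioid 200 | Opioid 20 | 100 × (20 − 200)/200 = −90% | 2 − 2 = 0 |
| Opioid 200 | Opioid 100 | −50% | 0 |
| Opioid 20 | Opioid 200 | 100 × (200 − 20)/20 = +900% | 0 |
| Opioid 200 | Opioid 5 plus a non-opioid | −97.5% (opioid) | 0 |
| Non-opioid 4000 | Non-opioid 400 | −90% | 1 − 1 = 0 |
| Opioid 5 | Non-opioid 400 | −100% (opioid) | 1 − 2 = −1 |
| Opioid 5 | None | −100% | 0 − 2 = −2 |
| None | Opioid 5 | New start | 2 − 0 = +2 |

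The first five rows are large dose changes that the shift table reports as stable. The last three involve a very small opioid dose and are reported as change. Shifts between other pain medication and none also register (1 − 0 = +1, 0 − 1 = −1), so the blind spot is change within a category, for opioids and non-opioids alike.

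**3. Documentation**

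Protocol 13.5 says that changes from the protocol's analysis are to be documented in the final SAP. SAP 7.4.9 gives no reason for omitting dose. SAP 9 records the added shift tables and the removed potency comparison, and nothing on dose.

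**4. What remains reported**

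SAP 7.3.2 gives tumor-pain analgesics their own tabulation and listing, and SAP 11 includes Listing 16.2.6.10. The medications can therefore be inspected subject by subject. What is missing is an aggregate summary of dose change.

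**The case against.** The strongest reply is that the objective is change in use, and a by-visit shift table does describe change in use, only more coarsely. Protocol 13.3.2.2.6 sets no metric, threshold or table, and Protocol 13.5 allows the SAP to alter protocol analyses. Coarse categories also avoid comparing doses of different opioids, for which SAP 7.7 has no conversion. Pain itself is covered by the QLQ-C30 symptom scales and the NIH questionnaire items (SAP 7.4.8).

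Much of this stands. It limits the weight of the point and supports keeping the shift table. It does not supply the dose evaluation that the protocol names, nor the documentation that Protocol 13.5 asks for.

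Four stronger readings are tempting, and the documents do not support them:

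- A reader might infer a large loss of statistical power. Neither document plans a test here, and any figure depends on invented inputs. Suppose 25 opioid users, a median dose fall of 40%, an SD of log dose ratio of 0.8 and no new starters. A two-sided sign test on stopping then needs at least 6 stoppers (2 × 0.5^6 = 0.031). If subjects stop after a fall over 75%, about 14% stop and power is about 12%. If they stop after a fall over 50%, about 41% stop and power is about 98%. A signed-rank test on dose has about 84% under the same assumptions, so the comparison can go either way.
- A reader might infer that only starting or stopping opioids registers. Shifts between other medication and none register too.
- A reader might infer that the dose information is lost. It is recorded and standardized, and the medications are listed.
- A reader might infer from the change log that a dose analysis was silently deleted. The log covers changes from SAP version 1.0, which is not available, so it cannot show whether that version held such an analysis.

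**Conclusion.** The point holds as a gap between protocol and SAP on a descriptive secondary endpoint. Protocol 13.3.2.2.6 evaluates change in total dose per tumor-pain medication. The SAP derives total daily dose but summarizes change only across three categories, and it does not document the omission. Every dose change within a category, in either direction, is summarized as no change.

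The size in subjects cannot be stated, because the documents give no figures on analgesic use or dose. The dose pairs above show how the rule behaves and do not estimate frequency. The primary endpoint and the trial's success criterion are unaffected. The change is worth making because it is cheap and restores the protocol's own evaluation.

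**What to change.** Keep the shift table. Add to SAP 7.4.9, and to the table list in SAP 11, one Full Analysis Set table of percent change from baseline in total daily dose for each tumor-pain medication at Months 3, 6, 9 and 12. Build it from the SAP 7.7 dataset, restricted to medications that the case report form identifies as given for tumor pain.

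State the baseline as use on the day of the first therapeutic dose. SAP 7.4.1 uses that day for antihypertensives, whereas neither 7.4.9 nor the pain-medication row of SAP Appendix 1 gives a baseline. Report counts of subjects in these categories:

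- stopped;
- decreased by at least 50% but still taking the drug;
- within 50% of baseline;
- increased by at least 50%, or newly started;
- switched to another drug.

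The 50% bands are a reporting choice. They mirror the per-drug rule of the primary endpoint and are not specified for analgesics in either document.

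The cost is SAP wording and one table from a dataset already planned. The downside is that switches between opioids must stand as a separate category, because the SAP has no equivalence table. If the sponsor prefers not to add the table, the SAP should state that the protocol's dose evaluation has been dropped and why, as Protocol 13.5 requires.
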